8.3.3.2 RELATIONSHIP TO STUDY INTERVENTION

All adverse events (AEs) will have their relationship to study intervention assessed by the Treating Therapist who examined and evaluated the participant based on temporal relationship and his/her clinical judgment. The degree of certainty about causality will be graded using the categories below:

- **Related** The AE is known to occur with the study intervention, there is a reasonable possibility that the study intervention caused the AE, or there is a temporal relationship between the study intervention and event. Reasonable possibility means that there is evidence to suggest a causal relationship between the study intervention and the AE.
- Not Related There is not a reasonable possibility that the administration of the study intervention caused the event, there is no temporal relationship between the study intervention and event onset, or an alternate etiology has been established.

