To compare the patient reported outcomes of iontophoresis with DSP in combination with PT versus iontophoresis with placebo in combination with PT versus PT alone in pediatric patients diagnosed with apophysitis of the knee.

To compare the safety of iontophoresis with DSP in combination with PT versus iontophoresis with placebo in combination with PT versus PT treatment alone in pediatric patients diagnosed with apophysitis of the knee.

Secondary Endpoints

- Patient reported percent difficulty with activities as measured by the LEFS
- Patient reported pain as measured by the FACES Pain Scale
- Patient reported activity as measured by the Godin Leisure-Time Activity Questionnaire
- Safety as measured by number and intensity of iontophoresis or DSP-related adverse events

Justification for Endpoints

- The LEFS is a validated patient reported outcome tool that assesses the patient's ability to perform 20 different activities involving the lower extremity. It allows the patient to rate his/her level of difficulty with each task as a result of pain or impairments to the involved lower extremity. The LEFS was selected based on its ease of administration and its inclusion of both common Activities of Daily Living (ADL's) and more advanced sport-specific activities.
- The FACES Pain Scale allows the pediatric patient to select the face that best represents his/her pain intensity. This is assumed to generate a more accurate pain rating than a quantitative estimation required with a numerical rating scale, where children may not all have a good understanding of the quantitative value of numbers. It has been documented that children prefer the FACES Scale to the Visual Analog Scale, which would require them to select a point on a horizontal line to indicate pain intensity. Using the FACES Pain Scale will allow Treating Therapists to track the patients' subjective pain ratings throughout the rehabilitation process.
- The Godin Leisure-Time Activity Questionnaire is a patient reported outcome tool that quantifies the patient's level of strenuous, moderate, and mild physical activity in a typical week. This provides the Treating Therapists with quantitative information regarding the

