8.3 ADVERSE EVENTS AND SERIOUS ADVERSE EVENTS

8.3.1 DEFINITION OF ADVERSE EVENTS AND SUSPECTED ADVERSE REACTION

Adverse event (AE) means any untoward medical occurrence associated with the use of an intervention in humans, whether or not considered intervention-related (21 CFR 312.32 (a)).

Suspected adverse reaction means any adverse event for which there is a reasonable possibility that the drug caused the AE. For the purposes of IND safety reporting, "reasonable possibility" means there is evidence to suggest a causal relationship between the drug and the AE.

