9 STATISTICAL CONSIDERATIONS

9.1 STATISTICAL HYPOTHESES

• Primary Efficacy Endpoint(s):

Length of time to meet RTS criteria as measured in days

Null Hypothesis: Time to achieve RTS criteria for Pediatric patients with apophysitis of the knee who receive iontophoresis with DSP and PT is the same as those who receive iontophoresis with placebo and PT or PT alone.

Alternative Hypothesis: Time to achieve RTS criteria for Pediatric patients with apophysitis of the knee who receive iontophoresis with DSP and PT will be different from those who receive iontophoresis with placebo and PT or PT alone.

• Secondary Endpoint(s):

Efficacy: Patient reported outcomes:

Null Hypothesis: There is not any significant difference in patient reported outcomes (LEFS, FACES pain scale, and Godin Leisure-Time Exercise) between pediatric patients with apophysitis of the knee who receive iontophoresis with DSP and PT and those who receive iontophoresis with placebo and PT or PT alone.

Alternative Hypothesis: Patient reported outcomes (LEFS, FACES pain scale, and Godin Leisure-Time Exercise) of pediatric patients with apophysitis of the knee who receive iontophoresis with DSP and PT will be different from those who receive iontophoresis with placebo and or PT alone.

Safety: Frequency and intensity of adverse events

Null Hypothesis: There is not any significant difference in frequency and intensity of adverse events between pediatric patients with apophysitis of the knee who receive iontophoresis with DSP and PT and those who receive iontophoresis with placebo and PT or PT alone.

Alternative Hypothesis: Frequency and intensity of adverse event among pediatric patients with apophysitis of the knee who receive iontophoresis with DSP and PT will be different from those who receive iontophoresis with placebo and PT or PT alone.

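### Section 8.3.3.2 lets a coincidental adverse event be both Related (by timing alone) and Not Related (by another known cause), with no rule for which prevails; this touches the related-event safety endpoint and the weekly report.

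*Combined protocol and SAP*

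**What the plan says.** All references are to the combined protocol and SAP.

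- **Who judges, and how.** Under Section 8.3.3.2 relationship is "assessed by the Treating Therapist who examined and evaluated the participant based on temporal relationship and his/her clinical judgment".
- **Related** (Section 8.3.3.2). Two alternatives come first: "The AE is known to occur with the study intervention, there is a reasonable possibility that the study intervention caused the AE". The third is "or there is a temporal relationship between the study intervention and event". No time window is given.
- **Not Related** (Section 8.3.3.2). The first alternative is the absence of a reasonable possibility of causation. The others are: "there is no temporal relationship between the study intervention and event onset, or an alternate etiology has been established".
- **Endpoint.** Section 3 lists as a secondary endpoint "Safety as measured by number and intensity of iontophoresis or DSP-related adverse events". The synopsis (Section 1.1) says the same.
- **Hypothesis and analysis.** The null hypothesis in Section 9.1 carries no such restriction: "There is not any significant difference in frequency and intensity of adverse events between pediatric patients". The GEE model in Section 9.4.4 is likewise described for adverse events in general.
- **Reporting.** In the Section 8.3.5 table, events judged related go to the Independent Safety Monitor weekly, and non-serious events go monthly.
- **Exposure.** Groups A and B receive at most two patches a week, up to 12 over at most eight weeks (Section 6.1.1). Group C receives none and is not blinded (Section 6.3).

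**The concern.** The two categories should divide events between them, and as written they overlap. Among children who are active and often ill, colds and minor injuries will occur during eight weeks of treatment. One that follows a patch and has an obvious other cause satisfies the last condition on each list. Two careful therapists can code it differently and both be following the protocol.

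Two things depend on the code. The first is the safety endpoint as worded in Sections 1.1 and 3, which counts related events only. If timing alone is enough, that count takes in background illness in both patch arms and the DSP-versus-placebo contrast weakens. Group C has no patch against which an event could be timed, so its background events may not enter the count, and comparisons with it could be tilted. The second is whether an event reaches the safety monitor in the weekly or the monthly report.

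**Working it through.** The plan states no figure on this point. The check is a logical one, followed by an illustration.

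**1. Do the definitions overlap?** Let K = known to occur with the intervention, R = reasonable possibility of causation, T = temporal relationship, E = alternate etiology established. Read literally:

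- Related = K or R or T
- Not Related = (not R) or (not T) or E

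Of the 2⁴ = 16 combinations, 12 meet both definitions, 2 meet only Related (R and T present, E absent, with K either way), 2 meet only Not Related (K, R and T all absent, with E either way), and none meets neither. The case at issue, T and E present with K and R absent, meets both. So does a timed event with no reasonable possibility and no other cause found (T only). This counts combinations, not events; it does not say how often the overlap will arise.

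**2. Dilution of DSP versus placebo, if related events are analysed.** The rates here are assumptions. Take true related events in 10% of DSP and 2% of placebo children, and let a share q of each arm have a coincidental event that counts by timing alone. Per arm, observed risk = 1 − (1 − p)(1 − q).

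| q | DSP | Placebo | Difference | Odds ratio |
|---|---|---|---|---|
| 0% | 10.0% | 2.0% | 8.0 points | (0.10/0.90)/(0.02/0.98) = 5.44 |
| 10% | 19.0% | 11.8% | 7.2 points | 1.75 |
| 20% | 28.0% | 21.6% | 6.4 points | 1.41 |
| 30% | 37.0% | 31.4% | 5.6 points | 1.28 |

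The risk difference shrinks only by the factor (1 − q). The odds ratio falls faster because the background raises both arms.

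A second assumed case, 20% versus 5% with 49 per arm and two-sided 0.05 (normal approximation), gives power of about 0.62 at q = 0, 0.37 at q = 10%, 0.25 at q = 20% and 0.18 at q = 30%.

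**3. Comparison with Group C.** Suppose there is no true harm and no Group C event can be coded related. If 10% of DSP children have a coincidental event coded related, the chance of a significant DSP-versus-PT-alone difference at 49 per arm is about 0.62 by the normal approximation, which is rough with zero events. By Fisher's exact test, 5 versus 0 gives p = 0.056 and 6 versus 0 gives p = 0.027, so at least 6 events are needed; P(Binomial(49, 0.10) ≥ 6) = 0.37. At 20% the two figures are 0.92 and 0.94. The direction is clear. The size depends on the assumed rate, the test, and how therapists code Group C events.

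**The case against.** **Clinical judgment settles it.** Section 8.3.3.2 tells the therapist to use judgment as well as timing, and a sensible therapist would code a cold with a known cause as Not Related. Section 10.1.7 provides adverse-event training, and under Section 8.3.5 the safety monitor checks accuracy. These will reduce disagreement. None of them says which category prevails when both are met, so the overlap stands.

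**The analysis does not use relatedness.** Sections 9.1 and 9.4.4 are worded for adverse events generally. Run that way, the coding does not alter the model. This stands and limits the point to the endpoint as worded in Sections 1.1 and 3 and to the weekly report.

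**The illustration is weak.** At 49 per arm, 10% versus 2% is about five children against one. Power before any dilution is only about 18% (Fisher) to 43% (uncorrected score test). The illustration also uses any event, whereas the endpoint is number and intensity. Both remarks are right; the table shows direction and mechanism, not an expected loss.

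A reader might also infer stronger things that the documents do not support:

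- *That the definition contradicts Section 8.3.1.* That section defines a different term: "Suspected adverse reaction means any adverse event for which there is a reasonable possibility that the drug caused the AE". A broader label for relatedness is not a contradiction.
- *That timing captures almost every on-treatment event.* That requires a window of several days, and the plan gives no window.
- *That the endpoint would reflect who scored it.* Therapists are blinded between the two patch groups and randomization is stratified by center (Section 6.3), so scoring differences between clinics mainly add noise to DSP versus placebo.
- *That true skin or drug reactions would be hidden.* All events are recorded with description, onset and severity (Section 8.3.4), burns are specifically watched for (Section 8.2), and severe or unexpected events are reported within 24 hours whatever their relationship (Section 8.3.5).

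**Conclusion.** The overlap is real and lies in the text: timing alone suffices for one category, another established cause suffices for the other, and nothing ranks them. It affects the related-event safety endpoint as worded in Sections 1.1 and 3, and the weekly report to the safety monitor. It does not affect the Section 9 safety model if that is run on all adverse events.

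If related events are analysed, timing-only coding pulls DSP versus placebo toward no difference and may bias comparisons with Group C. The size cannot be stated, because the plan gives no adverse-event rates; the fall in odds ratio from 5.4 to between 1.75 and 1.28 rests wholly on the assumed 10%, 2% and 10–30%. A reader might conclude that the safety endpoint will fill with coincidental illness. The documents support only that it can, and only under the related-event reading. The point merits correction because the rule is ambiguous and cheap to mend, not because a wrong safety conclusion has been shown.

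**What to change.** 1. **Make the categories exclusive in Section 8.3.3.2.** Suggested text: *Related: causation by the study intervention is a reasonable possibility; timing supports this judgment but is not sufficient alone. Not Related: causation is not a reasonable possibility. This includes any event with an established alternate etiology, which prevails where both categories could apply.* Carry the same text into the adverse-event form instructions.
2. **Reconcile Sections 1.1 and 3 with Sections 9.1 and 9.4.4** by stating whether the safety analysis uses all adverse events or related ones. Without this, the first change may alter no analysis.
3. **Re-read events already logged once under the single rule**, from records with group assignment masked, including Group C. Masking has to be arranged: Section 6.3 describes blinding of therapists and patch-group participants, and the plan does not say that the Principal Investigator is blinded.

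The cost is a few sentences and one masked re-read. Fewer events will be labelled related, and fewer will go in the weekly report, but none is lost: Section 8.3.4 has every event recorded whatever its relationship.

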8.3.3.3 EXPECTEDNESS

The Treating Therapist who examined and evaluated the participant will be responsible for determining whether an AE or suspected adverse reaction is expected or unexpected. An AE or suspected adverse reaction will be considered unexpected if the nature, severity, or frequency of the event is not consistent with either:

- The known or foreseeable risk of adverse events associated with the procedures involved in the research that are described in (a) the protocol-related documents (the IRB-approved research protocol and the current IRB-approved informed consent document), and (b) other relevant sources of information, such as product labeling and package inserts; or
- The expected natural progression of any underlying disease, disorder, or condition of the subject(s) experiencing the adverse event and the subject's predisposing risk factor profile for the adverse event. Whether or not the event is consistent with risk information described in the device package insert, drug package insert, or consent form.

8.3.4 TIME PERIOD AND FREQUENCY FOR EVENT ASSESSMENT AND FOLLOW-UP

The occurrence of an AE or serious adverse event (SAE) may come to the attention of study personnel during study visits, during the 30-day follow up phone call or from the 90-day electronic survey. AEs will be assessed at each treatment visit through the performance of a brief physical exam, interview by the Treating Therapist, review of concomitant medications, as well as from patient-reported responses to the FACES Pain scale and LEFS (assessed only at Study Treatment Visit 1, 5, 12, and 30-day follow-up).

All AEs including local and systemic reactions not meeting the criteria for SAEs will be captured on the appropriate case report form (CRF). Information to be collected includes event description, time of onset, clinician's assessment of severity, relationship to study product (assessed only by those with the training and authority to make a clinical assessment), expectedness, and time of resolution/stabilization of the event. All AEs occurring while on study will be documented appropriately regardless of relationship. All AEs will be followed to adequate resolution or stabilization.

Any medical condition that is present at the time that the participant is screened will be considered as baseline and not reported as an AE. However, if the study participant's condition deteriorates at any time during the study, it will be recorded as an AE.

Changes in the severity of an AE will be documented to allow an assessment of the duration of the event at each level of severity to be performed. AEs characterized as intermittent require documentation of onset and duration of each episode.

The treating Therapist will record all reportable events with start dates occurring any time after informed consent is obtained until 90 days after RTS criteria met or participant has received study treatment for eight (8) weeks, whichever is the shorter of the two time periods. At each study visit, the treating Therapist will inquire about the occurrence of AE/SAEs since the last visit. Events will be followed for outcome information until resolved or deemed by PI and Independent Safety Monitor as chronic or stable.

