- FACES Pain Scale (see Appendix 12.2) a patient reported paper-based questionnaire that asks the patient to choose the face that best represents the pain they are experiencing in their knee. Assessed at the end of each Study Treatment Visit and again at the end of the Clinic Check Visit.
- RTS Criteria Checklist (see Appendix 12.3) a paper-based checklist completed by the Treating
 Therapist to determine whether or not the participant is ready to safely return to sport. The
 checklist was created to include the basic movements typically required for sports activities,
 though these activities are also applicable for return to PE participation and free play, making it
 appropriate for all patients, even those not involved in organized sports. These movements
 include squatting, running, bilateral and unilateral jumping, back pedaling, and quick direction
 changes. The checklist includes qualifying criteria for proper mechanics and requires that all
 activities be pain-free. The checklist was created to assess readiness for sports participation
 without actually requiring that the patient return to sport participation to meet criteria, as not
 all patients participate in organized sports or are in-season year round. The items assessed as
 part of this checklist are all part of normal standard of care for physical therapy. Assessed at
 each Study Treatment Visit and again at the Clinic Check Visit.
- Godin Leisure-Time Exercise Questionnaire (see Appendix 12.4) a paper-based subject self-reporting questionnaire comprised of four (4) items that address the amount of time an individual engages in mild, moderate, and strenuous leisure time physical activity of at least 15 minutes in duration during a typical week. Assessed at Study Treatment Visit 1 and at the 30-day phone follow-up (see Appendix 12.5 30-Day Phone Follow Up) and 90-Day Follow-Up (see appendix 12.6 90-Day Follow-Up Electronic Survey).
- Study Treatment:
 - Iontophoresis (Groups A and B only) ~ 3 minutes in clinic and 2 hours at home The iontophoresis patch will be applied by a trained therapist in blinded fashion for all participants assigned to groups A and B (see section 6.1.2 Dosing and Administration). Performed at Study Treatment Visits 1 12 (Maximum of 12 treatments, maximum of 8 weeks since first Study Treatment Visit, or when RTS criteria are met and confirmed at the Clinic Visit Check, whichever is sooner).

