9.4.3 ANALYSIS OF THE SECONDARY ENDPOINT(S)

For each secondary endpoint:

A Generalized Estimation Equation (GEE) Model, including baseline records, will be used to check for changes in LEFS, FACES pain scale, and Godin Leisure-Time Exercise between treatment groups over time. Results for LEFS and Godin Leisure-Time Exercise will be presented as mean with 95% confidence interval, and results for FACES pain scale will be reported as odds ratio and 95% confidence interval.

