9.4.4 SAFETY ANALYSES

A GEE model will be conducted to estimate likelihood of occurring and intensity of adverse events for Pediatric patients with apophysitis of the knee who receive iontophoresis with DSP treatment and PT as compared to those who receive placebo or PT alone.

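### The planned safety comparison pools worsening of the treated knee with skin reactions, which dilutes, and can partly offset, a local harm of DSP; all versus related events is also left unreconciled

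*Combined protocol and SAP*

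**What the plan says.** **How events are found and recorded (8.3.4).** Events are assessed at treatment visits by brief exam, interview and medication review, "as well as from patient-reported responses to the FACES Pain scale and LEFS". A condition present at screening counts as baseline, but "if the study participant's condition deteriorates at any time during the study, it will be recorded as an AE". No threshold is set and the index knee is not excepted. Relatedness does not limit recording: "All AEs occurring while on study will be documented appropriately regardless of relationship".

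**What the scales are for.** FACES asks for "the face that best represents the pain they are experiencing in their knee" (8.1). FACES and LEFS are secondary efficacy endpoints with their own model, which "will be used to check for changes in LEFS, FACES pain scale, and Godin Leisure-Time Exercise between treatment groups over time" (9.4.3).

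**What the safety analysis takes in.** The null hypothesis in 9.1 reads "There is not any significant difference in frequency and intensity of adverse events between pediatric patients with apophysitis of the knee", comparing DSP with placebo or PT alone. Section 9.4.4 says "A GEE model will be conducted to estimate likelihood of occurring and intensity of adverse events". Neither limits events by relatedness or splits them by type. The safety endpoint in the synopsis (1.1) and Section 3 is narrower: the number and intensity of events related to iontophoresis or DSP.

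**Relatedness (8.3.3.2).** A temporal relationship alone is enough for Related. An established alternate etiology is enough for Not Related. The treating therapist decides, from timing and clinical judgment.

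**The concern.** Apophysitis of the knee is aggravated by running and jumping (2.1), and the return-to-sport checklist (12.3) tests jumping, hopping and a modified T-test. Some participants in any arm may therefore get worse for a time, and DSP is given to speed recovery. Under 8.3.4 that worsening goes on the same log as burns and rashes, and 9.4.4 sums over the log.

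Two things follow. If worsening is equally common in all arms, it adds noise and shrinks the visible difference in skin events. If DSP reduces worsening, the fall in one type of event offsets a rise in the other. Section 2.3.3 names local cutaneous and hypersensitivity reactions as the side effects of most concern, yet skin reactions have no planned analysis of their own. Intensity is affected too, since the Severe grade in 8.3.3.1 includes events that interrupt usual daily activity, and knee pain can do that.

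Section 9.4.7 allows early termination to be considered when the primary efficacy or safety outcome crosses its adjusted limit. A pooled safety outcome could mask a skin harm at such a look, or cross because of knee symptoms.

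**Working it through.** **1. The plan's own figures.** Section 9.2 gives 126 participants for the primary endpoint (f = 0.28, 80% power, alpha 0.05). Three-group one-way ANOVA, non-central F with 2 and N − 3 degrees of freedom and non-centrality N·f², gives 80.02% at N = 126, so this reproduces. 126 × 1.15 = 144.9, which becomes 147 (49 per group) when rounded up to a multiple of three. The 108 for safety cannot be checked, because no event rate or effect size is stated.

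**2. Does the related-only limit settle the matter?** A knee flare shortly after a patch meets the temporal clause and can be Related. The same flare can be put down to apophysitis and be Not Related. Iontophoresis is given up to twice weekly (6.1.1), so closeness in time will be common. In the PT-alone arm, with no iontophoresis, a related event has no clear meaning, yet 9.1 and 9.4.4 include that arm. The limit leaks, and 9.1 and 9.4.4 do not apply it.

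**3. Illustration of size.** From the plan: 49 per arm (9.2), two-sided 0.05 (9.4.1). Assumed, since the documents give no rates: skin events s = 25% on DSP and 5% on placebo; knee-worsening rates k as listed below; independence of the two. A comparison of participants with any event stands in for the GEE.

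- Any-event rate: p = 1 − (1 − s)(1 − k).
- Power = Φ[(|p₁ − p₂| − 1.96·SE₀)/SE₁], with SE₀ = √[p̄(1 − p̄)·2/49] and SE₁ = √{[p₁(1 − p₁) + p₂(1 − p₂)]/49}.

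Skin events alone: p̄ = 0.15, SE₀ = 0.0721, SE₁ = 0.0693; (0.20 − 0.1414)/0.0693 = 0.85; power 80%.

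Worsening 20% in both arms: 1 − 0.75 × 0.80 = 0.40 and 1 − 0.95 × 0.80 = 0.24. SE₀ = 0.0942, SE₁ = 0.0928; (0.16 − 0.1847)/0.0928 = −0.27; power 40%.

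Worsening 10% on DSP, 20% on placebo: 1 − 0.75 × 0.90 = 0.325 and 0.24. SE₀ = 0.0910, SE₁ = 0.0906; (0.085 − 0.1783)/0.0906 = −1.03; power 15%.

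| Knee worsening, DSP / placebo | Any event, DSP / placebo | Difference (points) | Power |
|---|---|---|---|
| none (skin only) | 25.0% / 5.0% | 20.0 | 80% |
| 20% / 20% | 40.0% / 24.0% | 16.0 | 40% |
| 5% / 10% | 28.8% / 14.5% | 14.3 | 40% |
| 10% / 20% | 32.5% / 24.0% | 8.5 | 15% |
| 15% / 30% | 36.3% / 33.5% | 2.7 | 5% |

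**4. When would cancellation be complete?** If DSP halves worsening, set 0.75(1 − k/2) = 0.95(1 − k). Then 0.575k = 0.20 and k = 35% on placebo. With skin events at 20% versus 5%, 0.55k = 0.15 and k = 27%.

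**The case against.** The strongest reply is that the endpoint covers only related events and that apophysitis is an obvious alternate etiology for index-knee pain. If the analysis followed the endpoint and therapists attributed flares to the disease, most of the problem would go. This stands in part: the limit is leaky, not void. It does not dispose of the point, because 9.1 and 9.4.4 do not carry the limit.

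A reader might infer that the safety comparison contains the efficacy outcome. The documents do not support that. Time to return to sport does not enter it, FACES and LEFS have their own model, and only deteriorations can become events. The two scales are two of five listed sources; a score change is not itself declared an event. FACES may also properly pick up pain from a burn.

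A reader might also infer that a pain benefit would cancel a skin harm. That depends on chosen rates. With skin events at 20% versus 5%, worsening of 25% in both arms gives 1 − 0.80 × 0.75 = 40.0% against 1 − 0.95 × 0.75 = 28.75%, so 11.25 of the 15 points survive. Worsening of 10% on placebo, halved by DSP, gives 24.0% against 14.5%, so 9.5 points survive. Pain already present at entry is not an event, and no worsening rate is documented. Both iontophoresis arms wear the same patch with the same current, so a large skin excess over placebo is an assumption.

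Nor would burns go unseen. Section 8.2 requires specific burn monitoring, each event is described and graded, and the Independent Safety Monitor receives related events weekly and cumulative reports monthly (8.3.5). What is missing is a planned between-arm analysis of them.

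**Conclusion.** The point holds as a defect of analysis and consistency. As written, the safety hypothesis and model pool knee worsening with skin reactions, and they disagree with the stated endpoint on whether unrelated events count. Pooling dilutes a skin difference even if DSP has no effect on the knee, and partly offsets it if DSP reduces worsening.

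In the illustration, power against a 25% versus 5% skin difference falls from about 80% to about 40% with equal worsening of 20%, and to about 15% if DSP halves that rate. These figures rest on assumed, independent event rates and a simple two-proportion comparison. They show direction and rough size and do not forecast this trial. Full cancellation needs placebo worsening of roughly 27% to 35% under the halving assumption. At 10% the signal is weakened, not cancelled. No sample size changes.

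**What to change.** 1. Reconcile the synopsis, Section 3, 9.1 and 9.4.4: state whether the safety model uses all or only related adverse events and, if related, what that means in the PT-alone arm.
2. In 9.4.4, keep the overall adverse event comparison. Add a pre-specified between-arm analysis of application-site (skin) reactions as their own category.
3. Tabulate separately, by arm, the events judged to be worsening of index-knee apophysitis.
4. Do not exclude an event merely because it was detected through FACES or LEFS. It may reflect a burn or other local reaction, and dropping it could discard a real harm.

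Recording and reporting of adverse events stay as they are. The cost is a few lines in the analysis section and one category flag on the adverse event log.
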